# **3.2. Definitions and Derivations**

The general definitions and derivations are listed in Table 2.

Terminology	Definition			
Safety Baseline	Safety baseline is the last visit in double blinded studies (810P301, 810P302, 810P503 and 810P204), which is visit 1 in 810P304.			
Efficacy Baseline (R- MOAS and CGI-S assessments)	Efficacy baseline is defined as the last non-missing value collected prior to the first dose of the SM in the double-blind studies (810P301, 810P302, 810P503 and 810P204).			
Study Day	Day 1 is defined as the date of safety baseline. For visits prior to safety baseline, Study Day is calculated as (Visit Date – safety baseline). For visits after study safety baseline, Study Day is calculated as (Visit Date – safety baseline +1).			

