1.4 Sponsor's Phase 3 Studies

The Sponsor is conducting two Phase 3 multicenter, randomized, double-blind, placebo controlled trials in a pediatric population of subjects 6-12 years of age and one in adolescents (12-17 years old) diagnosed with ADHD and IA (810P301, 810P302 and 810P503, respectively). The primary objective of these studies is to assess the efficacy and safety of SPN-810 in reducing the frequency of IA behaviors in pediatric and adolescent patients with ADHD when taken in conjunction with standard ADHD treatment. The Sponsor has recently developed a new measurement tool to assess the frequency of the behaviors associated with IA (Sponsor Study 810P501). This instrument is an electronic observer-reported outcome (eOBsRO) diary that monitors the occurrence of IA behaviors. Severity of IA is assessed using the Clinical Global Impression scales completed by both the caregiver and the Investigator.

Additional secondary endpoints include the assessment of subjects and caregivers quality of life using the Child Health Questionnaire Parent Form 28-item (CHQ-PF28) and the Parenting Stress Index-Short Form (PSI-4-SF) or the Stress Index for Parents of Adolescents (SIPA). The effect of molindone on body composition, metabolic parameters, prolactin and possible drug-drug interaction is also evaluated.

Children 6 to 12 years of age with ADHD and the associated feature of IA are randomized, with 97 subjects in each treatment arm (18 mg, 36 mg and placebo). [REDACTED]

[REDACTED]. After completing the two-week titration phase and the three-week maintenance phase, subjects will have the option to enroll in the OLE study (this study 810P304), at which time they will enter either the conversion phase or the tapering phase prior to the completion of the double-blind study. Subjects who choose to participate in this OLE will be converted from their maintenance study dose to a dose of 18 mg/day SPN-810 in a blinded fashion.

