3.2.1 Baseline Phase

There will be no screening period. Subjects may enter the study upon completion of one of the following double-blind studies: 810P301, 810P302, 810P503 or 810P204. Prior to conducting any procedures, written informed consent/assent must be obtained from the parent or LAR, and subject (when required). Inclusion and exclusion criteria will be re-assessed to confirm the subjects' eligibility. Each eligible subject will be assigned the same subject number used in the previous double-blind randomized study.

- Subjects who have completed one of the double-blind randomized studies (810P301, 810P302, 810P204 or 810P503) will be converted during their last week of participation and will initiate dosing [REDACTED] respectively.
- On a case-by-case basis, subjects who discontinued early during the maintenance phase of 810P301, 810P302, 810P204 or 810P503 and are approved for participation in this study will initiate at [REDACTED] respectively.

- In rare occasions, subjects who have discontinued early from the maintenance phase of 810P301, 810P302, 810P204 or 810P503 and have washed out from the study medication for at least 2 days may be approved to enroll in the OLE. These subjects will enter the study at [REDACTED] and gradually titrated up to an optimized dose.

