Prior to conducting any procedures, written Informed Consent must be obtained from the parent or LAR, and, if appropriate, Informed Assent from the subject. Visit 7 of 810P301 or 810P302, Visit 8 for 810P503 and Visit 6 of 810P204 will be Visit 1 of the OLE. Subjects who meet the requirements for study participation will begin titration at Visit 6 of 810P301 or 810P302 studies and at Visit 5 for the 810P204 study to the dose level of [REDACTED]. Subjects who have completed 810P503 study participation will start titration at Visit 7 to the initial dose of [REDACTED] in this study. Subjects will receive instructions and begin the study at their designated dose and will then continue on their optimized dose until the subject discontinues. The SM dose may be adjusted throughout the study upon the Investigator's discretion.

The following procedures will be performed at Baseline or Visit 1:

1. Obtain written informed consent and assent.
2. Perform physical examination
3. Perform 12-lead ECG
4. Confirm Inclusion/Exclusion criteria
5. Record socio-demographic information
6. Record vital signs (Heart Rate (HR), Blood Pressure (BP), temperature, and Respiratory Rate (RR))
7. Record height, weight and BMI
8. Collect blood samples for hematology, chemistry and pharmacogenomic testing (when applicable)
9. Collect urine sample for drug screen
10. Administer Investigator CGI-S
11. Administer Investigator and Caregiver CGI-I
12. Dispense SM
13. Administer Columbia Suicide Severity Rating Scale (C-SSRS)
14. Collect urine sample for pregnancy test (Females of Child Bearing Potential (FOCBP) only) and urinalysis
15. Assess and record concomitant medications
16. Collect and assess adverse events
17. Administer safety scales (Simpson-Angus, Barnes Akathisia, AIMS)

4.2.2 Visit 2

Visit 2 will occur approximately 2 weeks (± 1 week) following Visit 1.

1. Record vital signs (HR, BP, temperature, and RR)
2. Record height, weight and BMI
3. Collect urine sample for pregnancy test (Females of Child Bearing Potential (FOCBP) only)
4. Administer C-SSRS
5. Administer Investigator CGI-S
6. Administer Investigator and Caregiver CGI-I
7. Administer safety scales (Simpson-Angus, Barnes Akathisia, AIMS)

8. Collect and assess adverse events
9. Dispense SM.
10. Assess and record concomitant medications
11. Assess treatment compliance

4.2.3 Visit 3

Visit 3 will occur approximately 2 weeks (± 1 week) following Visit 2 according to the Schedule of Visits and Procedures.

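### Every safety change score starts from OLE Visit 1, when converting completers are already on SPN-810; no safety table gives a pre-drug reference or a split by prior arm

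*SAP*

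**What the plan says.** SAP 3.2, Table 2, gives two baselines. For safety: "Safety baseline is the last visit in double blinded studies", identified there as Visit 1 of 810P304. For R-MOAS and CGI-S: "Efficacy baseline is defined as the last non-missing value collected prior to the first dose of the SM in the double-blind studies". Protocol 6.1 names the same visit as the SAP for variables in general, and Protocol 6.8 does so for the EPS scales.

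The safety baseline feeds change from baseline in SAP 5.2.1 (laboratory), 5.3.1 (vital signs and body size), 5.4.1 (ECG) and 5.6 (EPS items). It also feeds the QTcF change categories in Appendix 9.2 and the denominator of the notable-QTcF table in 5.4.2. SAP 3.1 presents all summaries by optimized dose group and overall. The only extra split in a safety table is by sex, for insulin and prolactin (5.2.1).

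On timing, Protocol 1.4 offers the OLE "After completing the two-week titration phase and the three-week maintenance phase", and says: "Subjects who choose to participate in this OLE will be converted from their maintenance study dose to a dose of 18 mg/day SPN-810". Protocol 3.2.1 says that completers "will be converted during their last week of participation and will initiate dosing". Protocol 4.2.1 says that subjects "will begin titration at Visit 6 of 810P301 or 810P302 studies and at Visit 5 for the 810P204 study", while OLE Visit 1 is Visit 7 of 810P301/302 and Visit 6 of 810P204. In 810P503, conversion starts at Visit 7 and OLE Visit 1 is Visit 8.

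**The concern.** Long-term safety is the primary objective (SAP Table 1). Change from a baseline taken on drug measures change since OLE entry, not change since starting SPN-810. For a measure that shifts within weeks and stays shifted, a mean change near zero from Visit 1 has two readings: the drug does nothing, or the effect was already there. For a former 36 mg subject later held at 18 mg/day, the change could even have the opposite sign to the drug effect, because part of a dose-related effect would recede after the step down.

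The omitted amount differs between former placebo and former active subjects, and the planned tables pool them within each optimized dose group. As planned, no OLE safety table shows how far a subject at month 6 or later has moved from his or her own pre-drug value.

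**Working it through.** **1. Time on drug at Visit 1 (810P301/302 completers).** Titration is 2 weeks, maintenance 3 weeks and conversion about 1 week.

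- Former active: 2 + 3 + 1 = about 6 weeks.
- Former placebo: 0 + 0 + 1 = about 1 week.

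Protocol 1.4 gives "97 subjects in each treatment arm (18 mg, 36 mg and placebo", so 3 × 97 = 291 per study, of whom 2 × 97 = 194 (66.7%) were randomized to active drug.

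**2. Which analyses are affected.** Change scores for laboratory values, vital signs, body size, ECG and EPS items all use Visit 1. None of the SAP safety sections has a pre-drug column or a prior-arm split. The plan states no figure for this point, so there is none to reproduce.

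**3. How much could be omitted (illustration only).** The documents give neither onset time nor dose response. Assume an effect proportional to dose with first-order onset, equal arms with equal rollover, and the optimized dose D held from Visit 1. With the effect x in mg-equivalents, current dose d, w weeks and half-time h weeks:

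x_new = d + (x − d) × 2^(−w/h)

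Apply the prior-arm dose (0, 18 or 36) for 5 weeks, 18 mg/day for 1 week (giving Visit 1), then D for 26 weeks.

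Worked case, h = 1:

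- Former placebo: 18 + (0 − 18) × 0.5 = 9.0.
- Former 18 mg: 18 × (1 − 1/32) = 17.44 at week 5, then 18 + (17.44 − 18) × 0.5 = 17.7.
- Former 36 mg: 36 × (1 − 1/32) = 34.88 at week 5, then 18 + (34.88 − 18) × 0.5 = 26.4.

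With D = 18, every arm reaches 18.0 at week 26. Change from Visit 1 is then +9.0, +0.3 and −8.4 for the same true effect.

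Share omitted = x(Visit 1) / x(week 26). The three-arm figure is the ratio of the arm means. Each cell is for D = 18 / 36 / 54 mg/day:

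| Half-time | x(Visit 1): placebo, 18, 36 mg arm | Three arms mixed | Former placebo | Former 36 mg |
|---|---|---|---|---|
| 1 week | 9.0, 17.7, 26.4 | 98% / 49% / 33% | 50% / 25% / 17% | 147% / 73% / 49% |
| 4 weeks | 2.9, 11.6, 20.4 | 65% / 33% / 22% | 16% / 8% / 5% | 113% / 57% / 38% |
| 13 weeks | 0.9, 4.9, 8.9 | 33% / 17% / 12% | 7% / 3% / 2% | 57% / 31% / 21% |

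Above 100% means that change from Visit 1 has the opposite sign to the drug effect.

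**4. Sensitivity.** With half the prior-arm dose during the 2 titration weeks, the mixed shares fall to 96% / 48% / 32%, 58% / 29% / 19% and 29% / 15% / 10%. For the former 36 mg arm at D = 18, the 1-week figure is still above 100% (142%), but the 4-week figure drops to 99%. The sign reversal is thus secure in this model only for fast onset.

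**5. A slow-accruing measure.** Protocol 1.3 reports a mean weight gain of 2.18 to 3.70 kg over 6 months in the earlier open-label extension, mostly attributed to growth. If that gain were linear over 26 weeks, the part before Visit 1 would be 2.18 × 6/26 = 0.50 kg to 3.70 × 6/26 = 0.85 kg for former active subjects, and 0.08 to 0.14 kg (× 1/26) for former placebo subjects, growth included. Most of a slow effect stays in the planned change score.

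**The case against.** The strongest reply is that this is a different question and not an error. Protocol and SAP agree on the baseline, and change since entry is a usual and coherent summary for an extension study. Early effects belong to the placebo-controlled feeder studies, where, as Protocol 1.4 says, "The effect of molindone on body composition, metabolic parameters, prolactin and possible drug-drug interaction is also evaluated". An uncontrolled change from a pre-drug value cannot separate drug from growth and time. Absolute values are tabulated by visit, QTcF has absolute categories, and laboratory values outside the normal range are flagged in listings. The percentages above come from assumptions that the documents do not support, and the largest pair the fastest onset with the lowest modelled dose.

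Most of this stands, and it is why the point is an improvement and not a fault. It does not close the gap. For former active subjects in 810P301/302, the feeder studies cover about 6 weeks, so they cannot show a subject's distance from the pre-drug value at month 6 or month 60. Absolute values pooled over prior arms do not give that within-subject change either. The SAP already uses a pre-drug reference for efficacy. For R-MOAS this is partly forced, since none is scheduled at Visit 1, but CGI-S is collected at Visit 1, so there it was a choice.

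Two practical objections also stand: the feeder studies' assessment schedules are not in the documents, and the planned Visit 1 tables would still mix prior arms.

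**Conclusion.** The concern holds. The only safety baseline is OLE Visit 1. Completers who convert from 810P301/302 are already on drug then, for about 6 weeks (former active) or about 1 week (former placebo), and no safety table supplies a pre-drug reference or separates the prior arms.

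The resulting understatement cannot be sized from the documents. Under the stated model, the mixed share omitted at month 6 runs from 12% (13-week half-time, 54 mg/day) to 98% (1-week half-time, 18 mg/day). It is largest for measures that move quickly and persist, and small for slow-accruing effects or effects of later dose increases. Absolute values and adverse event incidence are not biased in this way.

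The exposure times apply to 810P301/302 completers only. Subjects from 810P503 convert before Visit 1 and enter at 36 mg/day. The 810P204 design is not given; its conversion is placed at Visit 4 in Protocol 3.1 and 3.2 but at Visit 5 in 4.2.1. These must be reconciled, although both precede Visit 1. Early discontinuers who have washed out are off drug at entry.

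**What to change.** Keep change from Visit 1 as planned. Add to SAP Table 2 a supplementary pre-drug safety baseline: the last available value before the first double-blind dose. For former placebo subjects, use the last value before the first SPN-810 dose where the feeder study measured one. Both are pre-drug values, so the omitted share becomes zero in every prior arm.

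Present change from this baseline for laboratory values, vital signs, body size, ECG intervals (including the QTcF change categories) and EPS items, for measures that the feeder studies collected. Show it separately by prior double-blind treatment, placebo or active, and do not pool the two. Add a footnote that these changes include growth and time effects.

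The cost is SAP wording, one extra set of tables, and a merge of feeder-study safety data. Subject numbers carry over (Protocol 4.3.4), and feeder data are already needed for the efficacy baseline, although that merge covers only R-MOAS and CGI-S. Before committing, confirm which measures 810P204 collected and whether former placebo subjects have values at the pre-conversion visit. Check pre-drug ECG availability in particular.

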#### Table 2: Definitions and Derivations

# **3.3.** Analysis Populations

The enrolled subjects consist of all subjects from any of the preceding double-blind studies (810P301, 810P302, 810P503 and 810P204) and meet the eligibility requirements.

#### SPN-810

The Safety Population includes all subjects who have signed Informed Consent/Assent forms and received at least 1 dose of SM in the 810P304 study.

The Safety Population will be used for all safety, efficacy and quality of life data analyses.

#### 3.4. Visit Windows

Data from scheduled visits will be analyzed. Visits will be analyzed as scheduled. Unscheduled measurements will be excluded from the descriptive statistics and statistical analyses but will be included in listings.

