Visit Number	EOS Visit ^a / Visit 1	Visit 2 (Week 2)	Visit 3 (Week 4)	Visit 4 (Week 8)	^b Visits 5 (Mo 3), 7, 9, 11, 13, 15, 17, 19, 21, and 23 (Mo 57)	^b Visits 6 (Mo 6), 8, 10, 12, 14, 16, 18, 20, 22, and 24 (Mo 60)	Visit 25
Window (Days)		2 weeks ±1 week from Visit 1	2 weeks ±1 week from Visit 2	4 weeks ±1 week from Visit 3	Visit 5 will occur 4 weeks ±1 week from Visit 4	Visit 6 will occur 3 months ± 1 week from Visit 5	
CHQ-PF28					X	X	X ^f
PSI-4-SF/SIPA ⁱ					X	X	X ^f
Safety Scales (Simpson-Angus, Barnes, AIMS)	X ^a	X	X	X	X	X	X
Adverse Events	X ^a	X	X	X	X	X	X
Concomitant Medications	X ^a	X	X	X	X	X	X
Drug Dispensation & Return	X ^a	X	X	X	X	X ^g	X
Drug Compliance		X	X	X	X	X	X

- a. Assessment is completed as the EOS visit in the preceding double-blind randomized study: Visit 7 (810P301 and 810P302), Visit 8 (810P503) and Visit 6 (810P204).
- b. Visit 7-24 will occur 3 months ±1 week from the previous visit. At each visit, a home urine pregnancy test will be distributed to female subjects of child-bearing potential. Subjects are required to complete testing 6 weeks after each visit. The site will follow-up with a call to record the results.
- c. Written consent and assent must be obtained prior to performing any 810P304 study-related procedures.
- d. To be performed for females subjects or childbearing potential prior administration of first dose of SM and will have to be tested as negative for the subjects to continue in the study.
- e. Heart rate (HR), blood pressure (BP), temperature, and respiratory rate (RR) will be measured.
- f. Assessments will be performed only for subjects who discontinue prior the end of the study
- g. Taper medication and instructions will be dispensed.
- h. Participation in PGx testing is optional. PGx Testing will be performed in subjects enrolling from the following studies: 810P301, 810P302 or 810P204. Subjects already enrolled, will provide a blood sample during the next visit after this amendment is effective.
- i. The SIPA scale will be administered only to subjects 13 to 17 years of age.

4.2.1 Baseline/Visit 1

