4.2.8 Visit 25 [(End of Study (EOS)] (Month 60 +/- 2 weeks)

Subjects who complete the study (60 months) will be instructed to down titrate for 2 weeks before returning to the office for the EOS Visit.

This document is confidential. It contains proprietary information of Supernus® Pharmaceuticals, Inc. Any viewing or disclosure of such information that is not authorized in writing by the Sponsor is strictly prohibited. Such information may be used solely for the purpose of reviewing or performing this study.

Subjects may discontinue prior the end of the study if the subject or the LAR withdraws assent and/or consent, or if the Investigator or the Sponsor decide it is no longer in the best interest of the subject. If the decision is made to discontinue early then the subject will be contacted and instructed to down-titrate at least 2 weeks prior to the EOS Visit.

The following procedures will be performed for subjects who complete the study (60 months) or discontinue early.

1. Perform physical examination
2. Perform 12-lead ECG
3. Collect urine sample for urinalysis and urine drug screen (all subjects), and pregnancy test (FOCBP only)
4. Record vital signs (HR, BP, temperature, and RR)
5. Record height, weight and BMI
6. Collect blood samples for hematology and chemistry
7. Administer C-SSRS
8. Administer safety scales (Simpson-Angus, Barnes Akathisia, AIMS)
9. Administer efficacy scales (R-MOAS, CGI-I and CGI-S, only for subjects who discontinue early)
10. Administer quality life scales (CHQ-PF28, PSI-4-SF or SIPA, only for subjects who discontinue early)
11. Collect and assess adverse events
12. Collect SM and assess treatment compliance
13. Assess and record concomitant medications

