4.6 Completion of Study and Discontinuation of Subjects

Subjects will be considered to have completed the study if they complete all visits up to and including the end of study visit. All subjects who discontinue early will be contacted by the study staff and instructed to down-titrate gradually over approximately 2 weeks prior to the EOS visit.

The Investigator(s) or subjects themselves may stop SM treatment at any time for safety or personal reasons. A subject is free to withdraw from the study at any time for any reason without prejudice to their future medical care by the physician or at the institution. The Investigator or Sponsor may also withdraw the subject at any time in the interest of subject safety. The withdrawal of a subject from the study should be discussed where possible with the Medical Monitor and/or the Investigator before the subject stops SM. Subjects removed from the study for any reason will not be replaced.

Reasons for withdrawal may include but are not limited to subject withdrawal of consent, occurrence of unmanageable AEs, or at the Investigator's discretion.

The primary reason for withdrawal must be recorded in the subject's medical record and on the eCRF. If a subject is withdrawn for more than one reason, each reason should be documented in the source document and the most medically significant reason should be entered on the eCRF.

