5.2.1 Retrospective-Modified Overt Aggression Scale (R-MOAS)

The Retrospective-Modified Overt Aggression Scale (R-MOAS) was developed to gauge the severity of aggressive behavior (Blader, 2010). Parents rate the frequency over the past week of 16 aggressive behaviors in four areas: verbal aggression; physical aggression toward others; aggression toward oneself; and destruction or hostile misuse of property. Numeric weighting amplifies the seriousness of more harmful behaviors in the total score. This assessment will be administered at each visit after the first 6 months (Visits 5 to 25). For subjects who discontinue early, this will be administered at the EOS (Visit 25).

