## 6. EFFICACY ANALYSES

Absolute value and CFB (if applicable) of efficacy endpoints will be analyzed descriptively at each scheduled visit by the optimized dose group and overall using the Safety Population, unless otherwise specified.

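### Visit 25 is both the Month 60 visit and the early-termination visit, and the SAP's by-visit tables do not separate the two

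*SAP*

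**What the plan says.** **How visits are analysed.** SAP 3.4 reads "Visits will be analyzed as scheduled" and leaves unscheduled measurements out of the summaries. It has no study-day windows and no separate early-termination visit. Study Day is defined in SAP 3.2 but is not used to place visits. By-visit summaries cover laboratory tests (SAP 5.2.1), vital signs and body size (5.3.1), ECG (5.4.1), the EPS scales (5.6) and C-SSRS (5.7). Efficacy endpoints are "analyzed descriptively at each scheduled visit by the optimized dose group and overall" (SAP 6), and SAP 7 treats quality of life the same way.

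**What Visit 25 is.** Protocol 4.2.8 is headed "Visit 25 [(End of Study (EOS)] (Month 60 +/- 2 weeks". The same section says "The following procedures will be performed for subjects who complete the study (60 months) or discontinue early". Protocol 5.2.1 adds, for R-MOAS, "For subjects who discontinue early, this will be administered at the EOS (Visit 25", and 5.3.1 to 5.3.3 repeat this for the quality-of-life scales. Under Protocol 4.6, "A subject is free to withdraw from the study at any time for any reason". A subject who leaves early is to be "instructed to down-titrate at least 2 weeks prior to the EOS Visit".

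**Who is rated there.** Footnote f of Protocol Table 1, repeated in SAP Appendix 9.1, is attached to CGI-S, CGI-I, R-MOAS, CHQ-PF28 and PSI-4-SF/SIPA at Visit 25: "Assessments will be performed only for subjects who discontinue prior the end of the study". Protocol 4.2.8, items 9 and 10, sets the same limit. Protocol 5.2.1 and 5.3.1 to 5.3.3, however, list R-MOAS and the quality-of-life scales for Visits 5 through 25 without that limit, and 5.2.2 has CGI done at every visit.

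**The concern.** One visit number stands for two different events. Because the protocol gives the early-termination assessment a scheduled visit number, the SAP's exclusion of unscheduled measurements does not remove it, and the nominal-visit rule puts it in the same column as the Month 60 end-of-study assessment.

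For safety, that column averages changes from baseline over very different times on study. Long-term safety is the primary objective and the subjects are growing. Protocol 1.3 reports mean weight gains of 2.18 to 3.70 kg over 6 months in the earlier open-label extension, most of it attributed to normal growth. A mean weight change at Visit 25 would therefore depend heavily on the mix of early leavers and completers. Protocol 6.8.3 also asks for changes in vital signs from baseline to final visit. The SAP names no such row, so Visit 25 is the column likely to be read in that role.

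For efficacy and quality of life, a column whose number the protocol ties to Month 60 would, under footnote f, contain nobody who reached Month 60.

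**Working it through.** The study has no power or sample-size calculation to reproduce. The checks are schedule arithmetic, a comparison of the texts, and an illustration of the mix.

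**1. The plan's own months.** Take Visit 5 at Month 3 and visits every 3 months after it: month of visit v = 3 + 3 × (v − 5). Visit 23 gives 3 + 54 = 57 and Visit 24 gives 3 + 57 = 60. Both match Protocol Table 1.

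**2. Visit 25 for a completer.** This is Visit 24 plus the 2-week taper. With 365.25 / 12 / 7 = 4.35 weeks per month, 60 + 2 / 4.35 = about Month 60.5. Counting Visit 5 from week 8 + 4 = week 12 (2.76 months) instead gives 2.76 + 57 + 0.46 = about Month 60.2.

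**3. Visit 25 for the earliest leavers.** This is the decision to stop plus 2 weeks. A stop just after the first dose gives week 2. A stop at week 1, the early edge of the Visit 2 window, gives week 3, or 3 / 4.35 = 0.69 months. These are cases that the schedule permits, not reported ones. The same visit number can thus cover about week 2 or 3 up to about Month 60.

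**4. Who is in each Visit 25 column, as written.**

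| Tables | Completers | Early discontinuers |
|---|---|---|
| Laboratory tests, vital signs and body size, ECG, EPS scales, C-SSRS | yes, after taper | yes, after planned taper, at any time on study |
| R-MOAS, CGI-S, CGI-I, CHQ-PF28, PSI-4-SF/SIPA | none (footnote f; 4.2.8 items 9 and 10) | yes, after planned taper, at any time on study |

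The second row needs no assumption about retention.

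**5. Share of the safety column that is early-termination data.** Let c be the proportion who complete 60 months and a the proportion of discontinuers who attend Visit 25, with all completers attending. Share = (1 − c)a / [(1 − c)a + c]. The documents give neither c nor a, so both are assumed.

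| Attendance a | c = 10% | c = 50% |
|---|---|---|
| 100% | 90/100 = 90% | 50/100 = 50% |
| 80% | 72/82 = 88% | 40/90 = 44% |
| 50% | 45/55 = 82% | 25/75 = 33% |

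**6. Where a last on-treatment value exists.** From Table 1, post-baseline laboratory tests start at Visit 4, and ECG, R-MOAS and quality of life start at Visit 5. Someone who leaves before those visits has no scheduled post-baseline on-treatment value for that measure.

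**The case against.** The strongest reply is that the Month 60 result is not in Visit 25 at all. Both schedules label Visit 24 as Month 60 and give Visit 25 no month; only the 4.2.8 heading does. Completers have R-MOAS, CGI, quality of life, laboratory tests and ECG at Visit 24, before taper, in a column of their own. No table shells are available, so the final labelling of Visit 25 is unknown. This stands, and it limits the point to one column.

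A reader might go further and infer that long-term safety changes are diluted throughout. The documents do not support that. By-visit columns up to Visit 24 remain specific to duration. Adverse-event tables (SAP 5.1) are not by visit, notable QTcF (5.4.2) counts any post-baseline value, and exposure (4.6) is shown by duration category.

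A reader might also infer that the Visit 25 efficacy column shows off-drug ratings in treatment failures. That too goes beyond the text. The taper is planned but adherence to it is not assured, and the interval from last taper dose to visit is not stated. The reasons for leaving in Protocol 6.5 include administrative ones and withdrawal of consent.

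Finally, Protocol 5.2.1, 5.2.2 and 5.3.1 to 5.3.3 can be read as rating completers at Visit 25. The conflict is real. The restriction is the better operative reading, because 4.2.8 states it and the SAP's own schedule repeats it, but the protocol does not settle the matter.

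**Conclusion.** The point holds for the Visit 25 column of the by-visit tables. As the SAP stands, the safety part of that column mixes early-termination and Month 60 assessments, and the efficacy and quality-of-life part contains only early discontinuers rated after a planned taper. The second statement rests on footnote f and 4.2.8 items 9 and 10 prevailing over the conflicting sections.

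The size of the mixture cannot be fixed from the documents. Over the assumed ranges it runs from 33% to 90% early-termination data. Some mixing occurs whenever at least one subject leaves early and attends the visit.

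All analyses are descriptive, so no error rate is affected, and individual data are listed. The harm is a misleading column, not missing Month 60 data. The change should be made, but it does not put the study's main safety tables in doubt.

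**What to change.** - In SAP 3.4, split Visit 25 by completion status into 'Early termination (post-taper)' and 'Month 60 EOS (post-taper)'. State which group takes a subject who declines a further 6-month period, since the documents do not say so clearly.
- Show early-termination efficacy and quality-of-life ratings in a separate table or block, outside the by-visit columns.
- Add a 'last on-treatment scheduled value' row for safety, efficacy and quality of life where such a value exists, and print its n. It cannot cover subjects who leave before Visit 4 (laboratory tests) or Visit 5 (ECG, R-MOAS, quality of life).
- Reconcile Protocol 5.2.1, 5.2.2 and 5.3.1 to 5.3.3 with 4.2.8 items 9 and 10 and footnote f on who is rated at Visit 25.

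The cost is SAP wording, one visit variable derived from disposition and visit dates, and slightly longer tables. The SAP changes need no new data.
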